visual performance was analyzed using a linear mixed model. Lens type was included as the only fixed effect. A compound symmetric (CS) covariance matrix was used to model the correlation between measurements on the same subject across study periods. Below is the variance-covariance matrix used in the visual performance model.

$$\sum_{\text{visual performance}} \begin{pmatrix} 0.003518 & 0.000374 & 0.000374 \\ 0.000374 & 0.003518 & 0.000374 \\ 0.000374 & 0.000374 & 0.003518 \end{pmatrix}$$

Acceptable Lens Fit

Acceptable lens fit is a binary response as y=1 if a subject eye has an acceptable fit and 0 otherwise. Indicated by the historical data there were no observed unacceptable lens fittings for either the Test or Control lens therefore, the common reference rate of 95% was selected for the sample size calculation, since this is considered to be a more conservative reference proportion. Assuming a correlation 0.80 between measurements within the same subject and period; and assuming a correlation of 0.50 between measurements within the same subject across periods. A total of 2000 replicating trials were simulated to estimate a sample size with a minimum statistical power of 80%.

Slit Lamp Findings

There were no Grade 3 or higher SLFs observed in any of the historical studies. Assuming no difference between study lenses and a correlation 0.80 between left and right eyes within the same subject and period; and a correlation of 0.50 between measurements within the same subject across periods (intra-subject correlation). A reference rate of no more than 10% was assumed (worse-case scenario) with a non-inferiority odds ratio margin of 2. A total of 2000 replicating trials were simulated, each replicated sample was analyzed using a generalized estimating equation (GEE) model with a binary distribution and the logit as the link function. Each model included lens type as the only fixed, eye was included as a random effect. The Odds ratio and corresponding 95% confidence interval was used estimate differences between the Test and Control lenses. The upper limit of each 95% confidence interval was compared to 2; if the upper limit was below 2 then NI=1; otherwise NI=0. Statistical power was calculated at the average NI. A sample size of 50 was chosen to achieve a minimum statistical power of 80%.

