5. STATISTICAL HYPOTHESES FOR STUDY OBJECTIVES

5.1. Primary Hypotheses

All primary hypotheses must be met in order to satisfy the primary objective of this study.

1. The Test lens will be non-inferior to the Control lens with respect to Distance Monocular logMAR Visual Acuity at the two-week follow-up evaluation under both lighting conditions (Bright illumination low contrast and dim illumination high contrast). A non-inferiority margin of 0.05 logMAR will be used.

2. The Test lens will be non-inferior to the Control lens with respect to the percentage of eyes with Grade 3 or higher Slit Lamp Findings (Biomicroscopy) across all follow-up visits (scheduled and unscheduled). A non-inferiority odds ratio margin of 2 will be used.
3. The proportion of eyes with acceptable fit will be greater than 90% across all visits (scheduled and unscheduled) for all subjects wearing the Test lens.
4. The Test lens will be non-inferior to the Control lens with respect to CLUE Overall Comfort at the two-week follow-up evaluation. A non-inferiority margin of -5 points will be used.
5. The Test lens will be non-inferior to the Control lens with respect to Vision satisfaction in bright lighting at the two-week follow-up evaluation. A non-inferiority cumulative odds ratio margin of 0.67 will be used.

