visual performance was analyzed using a linear mixed model. Lens type was included as the only fixed effect. A compound symmetric (CS) covariance matrix was used to model the correlation between measurements on the same subject across study periods. Below is the variance-covariance matrix used in the visual performance model.

$$\sum_{\text{visual performance}} \begin{pmatrix} 0.003518 & 0.000374 & 0.000374 \\ 0.000374 & 0.003518 & 0.000374 \\ 0.000374 & 0.000374 & 0.003518 \end{pmatrix}$$

Acceptable Lens Fit

Acceptable lens fit is a binary response as $y=1$ if a subject eye has an acceptable fit and $y=0$ otherwise. Indicated by the historical data there was only 1 observed unacceptable lens fittings for the Test lens therefore, the common reference rate of 95% was selected for the sample size calculation, since this is considered to be a more conservative reference proportion. Assuming a correlation 0.80 between measurements within the same subject and period (intra-eye correlation); and assuming a correlation of 0.50 between measurements within the same subject across periods. A total of 2000 replicating trials were simulated to estimate a sample size with a minimum statistical power of 80%.

Slit Lamp Findings

There were no Grade 3 or higher SLFs observed in any of the historical studies. Assuming no difference between study lenses and a correlation 0.80 between left and right eyes within the same subject and period; and a correlation of 0.50 between measurements within the same subject across periods (intra-subject correlation). A reference rate of no more than 5% was assumed (worse-case scenario) with a non-inferiority odds ratio margin of 2. A total of 2000 replicating trials were simulated, each replicated sample was analyzed using a generalized estimating equation (GEE) model with a binary distribution and the logit as the link function. Each model included lens type as the only fixed, eye was included as a random effect. The Odds ratio and corresponding 95% confidence interval was used estimate differences between the Test and Control lenses. The upper limit of each 95% confidence interval was compared to 2; if the upper limit was below 2 then NI=1; otherwise NI=0. Statistical power was calculated at the average NI. A sample size of 50 was chosen to achieve a minimum statistical power of 80%.

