The non-inferiority odds ratio margin of 2 corresponds to no more than a 5% difference between the Test and Control lenses assuming the Control reference rate does not exceed 5%.

Individual Questionnaire Items

Overall quality of vision outdoors and vision satisfaction in bright lighting sample size estimates were calculated using historical data from [REDACTED]. One-thousand boot strap samples were simulated based on the historical data. For each replicated sample a generalized linear mixed model was used with a multinomial distribution and the cumulative logit as the link function. Lens wear sequence, lens type, period and first order carryover effect were included in the model as fixed effects. A variance component (VC) covariance structure was used to model the measurements between subjects across study periods.

The non-inferiority cumulative odds ratio margin of 0.67 corresponds to no more than a 10% difference between the Test and Control lenses assuming there is no difference between study lenses.

Table 11: Sample Size Estimates and Power Calculations for Primary Endpoints

Endpoint	Number per Subjects to Complete	Power
Distance Monocular Visual Acuity (logMAR)	4	80%
SLFs (Grade 3 or Higher)	50	80%
Acceptable lens Fit	65	80%
CLUE Comfort	30	87%
Vision Satisfaction in Bright Lighting	48	81%

Table 12: Sample Size Estimates and Power Calculations for Secondary Endpoints

Endpoint	Number per Subjects to Complete	Power
CLUE Handling	30	81%
CLUE Overall Quality of Vision	30	82%
Overall Quality of Vision Indoors	95	81%

As indicated in Table 11 and 12 above, the sample size chosen for this study was primarily driven by overall quality of vision indoors. The plan is to enroll 120 eligible subjects with a target of 105 subjects to complete the study. During the enrollment period, the subject drop-out rate will be closely monitored, if an unexpectedly high dropout rate is observed, then the targeted total enrollment number may be increased accordingly to ensure that a minimum of 105 subjects complete the study.

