$$\mu_{ijklmn} = \beta_0 + \beta_1 Lens_{ij[k,l]} + \beta_2 \text{Baseline SLF}_1 + \beta_3 period_{k1} + \beta_4 period_{k2} + \beta_5 \text{sequence}_k + \beta_6 Carry1_{i[k,l]} + \gamma_m + \delta_{n_{(m)}} + \alpha_{j_{(n(m))}}$$

We assume the random subject eye effects are i.i.d as $\alpha_{j_{(n(m))}} \sim N(0, \sigma_{eye/subject/site}^2)$ for eye nested within subject within clinical site, the random effect for subject are i.i.d as $\delta_{n_{(m)}} \sim N(0, \sigma_{subject/site}^2)$ for subject nested within clinical site and the random clinical site effects are i.i.d as $\gamma_m \sim N(0, \sigma_{site}^2)$ for $i=1,2$ (lens), $j=1, 2$ (eye) , $k=1, 2, 3$ (period) $l=1, 2$ (Sequence) $m=1, \dots, 6$ (Site) $m=1, \dots, n_m$ (subject/site).

In this model, the lens I will be determined by the period k and sequence l, therefore i is denoted as a function of j and k. We define $Lens_i=0$ for the Control lens and $Lens_i=1$ for the Test lens. The odds ratio for having a lower rate of SLFs can be written as $OR=e^{\beta_1}$.

For the β coefficients, independent non-informative priors $N(0, 10000)$ will be used. For the variance of random effects of $\sigma_{eye}^2, \sigma_{subject}^2$ and σ_{site}^2 , independent non-informative conjugate priors inverse-gamma (0.001, 0.001) will be used. The Metropolis-Hastings algorithm as implemented in the SAS/STAT 14.2 PROC MCMC procedure will be used to estimate posterior distributions of the unknown parameters. Inferences will be made based on the posterior credible interval for the relevant parameters.

Hypothesis Testing

The null and alternative hypothesis for Non-inferiority is as follows:

$$H_o: OR \geq 2$$

$$H_A: OR < 2$$

Where OR represents the cumulative odds of the Test lens having a lower rate of Grade 3 SLFs compared to the Control lens and is calculated as $OR=e^{\beta_1}$. Non-inferiority will be established if the upper limit of the 2-sided 95% credible interval is below 2, i.e. $P(OR < 2 | y)=0.975$.

If the full planned model fails to converge, reduced versions may be considered. In the event that the number of Grade 3 or higher SLFs is too small Grade 2 or higher SLFs will be analyzed and tested as described above.

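### The slit lamp margin of 2 is justified and powered on the population odds ratio but tested on a conditional one, so the planned test is stricter than the one that was powered

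*SAP*

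**What the plan says.** SAP 5.1 states the hypothesis "with respect to the percentage of eyes with Grade 3 or higher Slit Lamp Findings (Biomicroscopy) across all follow-up visits" and adds: "A non-inferiority odds ratio margin of 2 will be used". All primary hypotheses must be met.

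SAP 8.4 puts the margin in percentage points: "The non-inferiority odds ratio margin of 2 corresponds to no more than a 5% difference between the Test and Control lenses", given a Control rate of at most 5%. For power, 2,000 trials were simulated and "each replicated sample was analyzed using a generalized estimating equation (GEE) model with a binary distribution and the logit as the link function". The next sentence adds that eye was a random effect. The upper 95% limit was compared with 2, and 50 subjects are said to give 80% power. The inputs are "Assuming no difference between study lenses and a correlation 0.80 between left and right eyes within the same subject and period" and 0.50 across periods. The SAP's reference rate is "A reference rate of no more than 5% was assumed (worse-case scenario"; Protocol 14.2 has "A reference rate of no more than 10% was assumed (worse-case scenario".

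SAP 11.1 tests something different. It fits a Bayesian logistic regression with random effects for site and subject (the formula also has eye within subject), defines the odds ratio as e^β1, and rules: "Non-inferiority will be established if the upper limit of the 2-sided 95% credible interval is below 2". Neither document converts the margin or averages the posterior over the random effects. If Grade 3 or higher findings are too few, Grade 2 or higher is tested in the same way.

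**The concern.** In a logistic model with random effects, e^β1 compares the two lenses for the same eye of the same subject. A percentage of eyes, and a margin argued in percentage points, describe the whole population. The two odds ratios agree only at 1 or when the random-effect variance is zero. Otherwise the conditional one is further from 1, and more so as the correlation within subject rises.

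Keeping the number 2 while changing the scale therefore tightens the test, and the GEE-based power does not describe it. At stake is a co-primary hypothesis: a Test lens equal to Control, or worse by less than the stated margin, can fail because of the scale.

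**Working it through.** **Inputs.** Margin 2, rate 5%, correlations 0.80 and 0.50, GEE logit, 50 subjects for 80% power, 105 completers (SAP 8.4); rate 10% (Protocol 14.2); sequences Test/Control/Control and Control/Test/Test (SAP 3.1). The SAP gives no random-effect variance and does not say whether its correlations refer to the binary outcomes or to a latent scale. Both readings are shown.

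**1. The margin on its stated scale.** Odds at 5% are 0.05/0.95 = 0.0526. Doubled they are 0.1053, a rate of 9.5% and a difference of 4.5 points, which agrees with SAP 8.4.

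**2. The plan's own power figure.** 50 subjects × 3 periods × 2 eyes, equal rates, binary correlations 0.80/0.50, lens-only logistic GEE, 2,000 trials per setting. Across choices of clustering, working correlation and standard error, power was 24% to 45% at 5% and 42% to 66% at 10%. In closed form, power = Φ(ln 2/SE − 1.96):
- 5%: SE 0.496, Φ(1.40 − 1.96) = 29%
- 10%: SE 0.360, Φ(1.93 − 1.96) = 49%

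So the stated 80% at 50 subjects does not reproduce even on the population scale. That is a separate fault. It means the comparison below must use recomputed power on both scales.

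**3. What a conditional odds ratio of 2 means for the population.** Choose a normal random intercept that gives the required rate and correlation, add ln 2, and average the probabilities.
- Binary correlation 0.50 at 5%: SD 3.91, and the rate rises from 5% to 6.88%. Odds ratio (0.0688/0.9312)/0.0526 = 1.40. At 10% (SD 3.44) it is also 1.40.
- Average pairwise binary correlation: a subject's six measurements form 15 pairs, 3 within a period and 12 across periods, so (3 × 0.80 + 12 × 0.50)/15 = 0.56. Result 1.35.
- Binary 0.80 throughout: 1.15.
- Latent 0.50: variance (0.5/0.5) × π²/3 = 3.29. The approximation exp[ln 2/√(1 + 0.346 × 3.29)] gives 1.61; integration gives 1.73 at 5% and 1.66 at 10%.
- Latent 0.80: variance 4 × 3.29 = 13.16. The approximation gives 1.34; integration gives 1.43 at 5% and 1.38 at 10%.

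The 0.80 links two eyes in the same period, whereas the lens comparison runs across periods. The values using 0.50 or 0.56 are therefore the more relevant ones.

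**4. Chance of passing with equal lenses, 105 completers.** The same simulated data were analysed by subject-clustered GEE and by a random-effects logit, each with the limit compared with 2. Ranges come from separate simulations.

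| Rate | Correlation reading | GEE | Random-effects e^β1 | Loss (points) |
|---|---|---|---|---|
| 5% | binary | 48-52% | 24-29% | 23-24 |
| 10% | binary | 77-78% | 39-41% | 36-38 |
| 5% | latent | 41-43% | 38-41% | 0-5 |
| 10% | latent | 68% | 53% | 15 |
| 16% | binary | 85-90% | 45-54% | 36-40 |
| 31% | binary | 98-99% | 61-63% | 36-37 |
| 16% | latent | 85% | 62% | 23 |
| 31% | latent | 94% | 78% | 16 |

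The 16% and 31% rows are the historical Grade 2 rates in SAP 8.4: 108/680 = 15.9% for Test and 83/270 = 30.7% for Control. They matter for the fallback endpoint. Applying 0.80/0.50 and equal lenses there is an assumption, because the SAP states those inputs for its Grade 3 simulation.

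**Limits.** The simulated random-effects model had lens and a subject intercept only. In closed form, period, sequence and carryover together raise the standard error by about 1%.

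**The case against.** The strongest reply is that SAP 11.1 defines its odds ratio openly as e^β1, and a subject-specific odds ratio is a legitimate crossover estimand. SAP 8.4 also gives the 5 points as an upper bound, which a stricter test still respects. And its GEE sentence is followed by a random effect for eye, so the power model is not cleanly a population one. All of this is fair, but none of it makes the GEE-based power apply to the planned test, and no margin is justified on the conditional scale.

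A second reply concerns the true effect. The historical Grade 2 rates favour Test, with a crude odds ratio of (108/572)/(83/187) = 0.43. With a simulated conditional SD of 0.39 and a scale ratio of 2.36, (0.693 + 2.36 × 0.855)/0.39 − 1.96 is about 5, so the planned test would pass more than 99% of the time. This stands as an indication only: the pooled groups are not fully paired, and SAP 8.4 itself assumes no difference for slit lamp findings.

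Third, SAP 11.1 allows reduced models if the full one does not converge, and dropping the random effects would remove the mismatch. But the meaning of the margin would then depend on which model happened to converge.

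A reader might infer three stronger claims that the documents do not support:
- **That the margin really tested is 1.34.** No such figure or variance appears. It is one value in a range that depends on an unstated correlation scale.
- **That power always falls sharply.** On the latent reading at 5% it barely moves.
- **That the two ordinal items (bright-light satisfaction, vision indoors) lose power in the same way.** SAP 8.4 powered the individual items with a mixed model on bootstrapped historical data, so a GEE-versus-mixed comparison under equal lenses does not apply.

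**Conclusion.** The mismatch is in the text. The margin of 2 is argued and powered for the population, then applied to a conditional coefficient. The planned test is stricter than the powered one, and the stated slit lamp power does not describe it.

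The size rests on how the 0.80/0.50 correlations are read, on equal lenses and on 105 completers. A conditional 2 corresponds to a population odds ratio of about 1.35 to 1.4 on the binary reading, within an overall range of about 1.15 to 1.7. At 5% and 10% rates the loss of power is roughly 23 to 38 points on the binary reading, and 0 to 15 on the latent one. At the historical Grade 2 rates it is about 35 to 40 points (binary) or 15 to 25 (latent). No Grade 3 or higher finding occurred in the historical studies, so the fallback may well be the endpoint actually tested.

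The direction is conservative. It would be wrong to read this as a weakness that lets an inferior lens through; the risk is that an equivalent lens fails a co-primary hypothesis. It should be fixed, but it does not threaten the validity of a positive result.

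**What to change.** - In SAP 11.1, name the population odds ratio as the slit lamp target. For each posterior draw, average the predicted probabilities over the random effects, with the other covariates handled identically for both lenses, to get one proportion per lens. Form the odds ratio and compare its 95% limit with 2. Say that the same rule holds for the Grade 2 fallback and for any reduced model. SAP 11.3 already forms the lens preference odds ratio from mean probabilities. The alternative is to make the subject-clustered GEE of SAP 8.4 the analysis.
- In SAP 8.4, recompute and restate the slit lamp power with the analysis actually planned. State whether 0.80 and 0.50 are binary or latent, and use one reference rate in both documents.
- Report the conditional odds ratio alongside.

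The cost is SAP wording, a post-processing step on the MCMC output and one new power simulation. The drawback is that the tested safety margin becomes wider than e^β1 below 2, though it is the margin the SAP justified. The restated power may also fall short of 80%.

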11.2. Secondary Analysis

Secondary efficacy analysis:

CLUE Overall Quality of Vision and Handling

CLUE Overall Quality of Vision and Handling will be analyzed and test in the exact same manner as CLUE Overall Comfort.

Overall Quality of Vision Indoors

Overall quality of vision indoors will be analyzed and tested in the same manner as vision satisfaction in bright lighting. The only difference between the two models are the response set used to assess each item. For this model,

Let $y_{ijklm} = (y_{ijklm1}, y_{ijklm2}, y_{ijklm3}, y_{ijklm4}, y_{ijklm5})$ denote the rating for the m^{th} subject, from the l^{th} site, assigned to the i^{th} study lens in the j^{th} period using the k^{th} sequence. Possible values of y_{ijklm} are 1 if the subject rating of overall quality of vision indoors are X and 0 otherwise (x=1 for Excellent and X=5 for Poor, respectively).

Secondary safety analysis:

Not Applicable

11.3. Other Analysis

Other efficacy analysis:

Lens Preferences:

Lens preference items listed below will be analyzed separately using Bayesian multinomial models for nominal data.

1. Overall lens preference
2. Overall comfort
3. Overall vision
4. Overall reduction of glare
5. Overall preference indoors
6. Overall preference outdoors
7. Overall preference while driving during the day
8. Overall preference while driving at night
9. Overall preference while using computer screens & digital devices

The regression models will include lens wearing sequence, age and gender as fixed covariates when appropriate. Investigational site will be included as random effect if the variation across sites is not negligible.

Let $y_{ijkl} = (y_{ijkl1}, y_{ijkl2}, y_{ijkl3}, y_{ijkl4})$ denote subject lens preference for the i^{th} subject from the j^{th} site with regard to the k^{th} preference item. Possible values of y_{ijkl} are: $y_{ijkl1} = 1$ if the subject preferred the Test lens, 0 otherwise; $y_{ijkl2} = 1$ if the subject preferred the Control lens, 0 otherwise; $y_{ijkl3} = 1$ if the subject preferred both the Test and Control lenses, 0 otherwise and $y_{ijkl4} = 1$ if the subject preferred neither Test nor Control lenses, 0 otherwise. The likelihood of y_{ijkl} is constructed as follow:

$$\begin{aligned}
 y_{ijkl} &\sim \text{Multinomial} (p_{ijkl1}, p_{ijkl2}, p_{ijkl3}, p_{ijkl4}) \\
 p_{ijkl1} &= \theta_{ijkl1} / \sum_m \theta_{ijkl1} \\
 \log(\theta_{ijkl1}) &= \mu_{0kl} + \beta_{1k} \text{Sequence}_{ij} + \beta_{2k} \text{Age}_{ij} + \beta_{3k} \text{Female}_{ij} + \delta_j
 \end{aligned}$$

where μ_{0kl} are the intercepts with μ_{0k4} set to 0, $p_{ijkl} = P(Y_{ijkl} = 1)$ and $\gamma_j \sim N(0, \sigma_s^2)$. We will use independent vague $N(0, 1000)$ priors for the regression coefficients μ_{0kl} , β_{1k} , β_{2k} and β_{3k} , and $IG(0.001, 0.001)$ for σ_s^2 .

Hypothesis Testing:

For each preference item, the null and alternative hypotheses for superiority are as follows:
 $H_0: OR_k \leq 1$ $H_a: OR_k > 1$; where OR_k represents the odds ratio of comparing the Test lens to the Control lens with regard to item k. The odds ratio is calculated as:

$$OR_k = p_{.k1}(1 - p_{.k2})/p_{.k2}(1 - p_{.k1}),$$

where $p_{.kl}$ is the mean estimate p_{ijkl} for $k=1, \dots, 5$ and $l = 1, \dots, 4$.

For each item k, the superiority will be declared if the lower bound of the 2-sided 95% credible interval of OR_k is greater than 1: $Pr(OR_k > 1 | \mathbf{y}) \geq .975$.

Outdoor Glare Reduction

Outdoor Glare reduction consists of 4 individual questionnaire items.

1. Ability to see comfortably in bright sunlight
2. Reduction in glare caused by bright sunlight
3. Reduction of squinting in bright sunlight
4. Reduction of eyestrain in bright sunlight

All outdoor glare items are assessed using the same ordinal scale (1=Excellent ... 5=Poor). Outdoor Glare reduction items will be analyzed separately using a Bayesian multinomial model for ordinal data adjusting for baseline. The regression model will include sequence of lens wear, lens type, period and first order carryover effect. Clinical site and subject nested within clinical site will be included as random effects. Other subject characteristics such as age, gender, race and iris category will be included when appropriate.

The Model:

Let $y_{ijklm} = (y_{ijklm1}, y_{ijklm2}, y_{ijklm3}, y_{ijklm4}, y_{ijklm5})$ denote the rating for the m^{th} subject, from the l^{th} site, assigned to the i^{th} study lens in the j^{th} period using the k^{th} sequence. Possible values of y_{ijklm} are 1 if the subject rating of outdoor glare items are X and 0 otherwise (x=1 for Excellent and X=5 for Poor, respectively). The likelihood is constructed as follows:

$$y_{ijklm} \sim \text{Multinomial}(P_{ijklm1}, P_{ijklm2}, P_{ijklm3}, P_{ijklm4}, P_{ijklm5})$$

$$P_{ijklm1} = \gamma_{ijklm1}$$

$$P_{ijklmX} = \gamma_{ijklmX} - \gamma_{ijklm(X-1)} \quad 2 \leq n \leq 4$$

$$P_{ijklm5} = 1 - \sum_{x=1..4} P_{ijklmX}$$

$$\text{Logit}(\gamma_{ijklm}) = \theta_n + \beta_1 \text{Lens}_{i[j,k]} + \beta_2 \text{Period}_{j1} + \beta_3 \text{Period}_{j2} + \beta_4 \text{Sequence}_k + \beta_5 \text{Carry}_{i[j,k]} + \gamma_l + \delta_{m(l)}$$

Where θ_n is the intercept for levels n=1,2,3,4, $P_{ijklm1} = \Pr(\gamma_{ijklm1} = 1)$ with respect to outdoor glare preference. We assume the random subject effects are independent identically distributed (i.i.d) as $\delta_{m(l)} \sim N(0, \sigma_{\text{subject}/\text{site}}^2)$ for subject m nested within clinical site l and the random clinical site effects are i.i.d as $\gamma_l \sim N(0, \sigma_{\text{site}}^2)$ for i=1,2 (lens), j=1, 2, 3 (Period) k=1, 2 (Sequence) l=1, ... 5 (Site) m=1, ... n_l (subject/site).

In this model, the lens I will be determined by the period j and sequence k, therefore i is denoted as a function of j and k. We define $\text{Lens}_i=0$ for the Control lens and $\text{Lens}_i=1$ for the Test lens. The odds ratio for having higher rating can be written as $OR = e^{-\beta_1}$.

Independent vague $N(0, 1000)$ priors for the regression coefficients β_i i=1,...5. For θ_n , we are considering the following priors

$$\begin{aligned}\pi_0(\theta_1) &\sim N(0, 100) \\ \pi_0(\theta_2 | \theta_1) &\sim N(0, 100) I(\theta > 0) \\ \pi_0(\theta_3 | \theta_2) &\sim N(0, 100) I(\theta > 0) \\ \pi_0(\theta_4 | \theta_3) &\sim N(0, 100) I(\theta > 0)\end{aligned}$$

For the variance of random effects independent vague normal priors will also be used; $\sigma_p^2 \sim \text{inverse-gamma}(0.001, 0.001)$ and $\sigma_s^2 \sim \text{inverse-gamma}(0.001, 0.001)$. The Metropolis sample algorithm as implemented in the SAS/Stat MCMC Procedure will be used to estimate the posterior distributions of the unknown parameters. Inferences will be made based on the posterior credible interval for the relevant parameters.

Hypothesis Testing

The null and alternative hypotheses for superiority are as follows:

$$\begin{aligned}H_0 \quad OR &\leq 1 \\ H_A \quad OR &> 1\end{aligned}$$

Where OR represent the cumulative odds ratio of having higher rating of the Test lens compared to the Control lens where the OR is calculated as $OR = e^{-\beta_1}$. Superiority will be declared if the lower bound of the 2-sided 95% credible confidence interval is above 1, i.e.

$$P(OR = e^{-\beta_1} > 1 | y) = 0.975.$$

Indoor Glare Reduction

Indoor Glare reduction consists of 4 individual questionnaire items:

1. Reduction in squinting while using computer screens or digital devices
2. Reduction in glare from the computer screen or digital devices
3. Reduction in glare caused by bright indoor lights
4. Reduction in glare caused by bright light coming through the window

Each item will be analyzed individually and tested in the exact same manner as the Outdoor Glare Reduction Items described above.

Driving Measures

Driving measure consists of two individual questionnaire items:

1. Reduction in glare while driving during the day
2. Reduction in glare while driving during the night

Each item will be analyzed individually in the exact same manner as the Outdoor Glare Reduction Items described above. However, the hypothesis test will be as follows:

Hypothesis Testing

The null and alternative hypotheses for superiority are as follows:

$$\begin{aligned} H_0 & OR \leq 0.67 \\ H_A & OR > 0.67 \end{aligned}$$

Where OR represent the cumulative odds ratio of having higher rating of the Test lens compared to the Control lens. Non-inferiority will be declared if the lower bound of the 2-sided 95% credible confidence interval is above 0.67, i.e. $P(OR=e^{-\beta_1}>0.67|y)=0.975$. Superiority will be declared if the lower bound of the 2-sided 95% credible interval is above 1, i.e. $P(OR=e^{-\beta_1}> 1|y)=0.975$. Superiority will only be tested in the event that non-inferiority is established.

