4.3. Other Endpoints

Lens Preferences

Lens preferences will be assessed by individual items regarding lens preference at the two-week follow-up of the second wearing period (Visit 3). Subjects will be asked to choose for each preference item one of the following responses: Strongly Prefer the first lens, Prefer the first lens, no preference, prefer the second lens, strongly prefer the second lens. Lens preference questions consist of:

1. Overall lens preference [REDACTED]
2. Overall comfort [REDACTED]
3. Overall vision [REDACTED]
4. Overall reduction of glare [REDACTED]

5. Overall preference indoors [REDACTED]
6. Overall preference outdoors [REDACTED]
7. Overall preference while driving during the day [REDACTED]
8. Overall preference while driving at night [REDACTED]
9. Overall preference while using computer screens & digital devices [REDACTED]
[REDACTED]

Driving Performance

Driving performance will be assessed by two individual patient reported outcomes (PRO) questions at the two-week follow-up evaluation. The individual items are as follows:

1. Reduction in glare while driving during the day [REDACTED]
2. Reduction in glare while driving during the night [REDACTED]

Indoor Performance

Indoor performance will be assessed by three individual items at the two-week follow-up evaluation. The individual items are as follows:

1. Reduction in glare from the computer screen or digital devices [REDACTED]
2. Reduction in glare caused by bright indoor lights [REDACTED]
3. Reduction in glare caused by bright light coming through the window [REDACTED]

Outdoor Performance

Outdoor performance will be assessed by four individual items at the two-week follow-up evaluation. The individual items are as follows:

1. Ability to see comfortably in bright sunlight [REDACTED]
2. Reduction in glare in bright sunlight [REDACTED]
3. Reduction in squinting in bright sunlight [REDACTED]
4. Reduction in eye strain in bright sunlight [REDACTED]

All driving, indoor and outdoor (PRO) items above will be assessed using the same excellence scale of; 0: Not Applicable, 1: Excellent, 2: Very Good, 3: Good, 4: Fair and 5: Poor.

Contrast sensitivity will also be evaluated during this study.

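### In the SAP's lens-preference model the sequence, age, sex and site terms cancel, and its four categories do not match the five answers collected

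*SAP*

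**What the plan says.** SAP 4.3 and protocol 2.2 give the same response set for each preference item, asked at Visit 3: "Strongly Prefer the first lens, Prefer the first lens, no preference, prefer the second lens, strongly prefer the second lens".

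SAP 11.3 sets the analysis: "Lens preference items listed below will be analyzed separately using Bayesian multinomial models for nominal data". The four indicators are Test preferred, Control preferred, a third equal to 1 "if the subject preferred both the Test and Control lenses, 0 otherwise", and a fourth equal to 1 "if the subject preferred neither Test nor Control lenses, 0 otherwise". The text says that the models include wearing sequence, age and gender where appropriate, and site as a random effect if its variation is not negligible.

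The log of theta for a category is "\mu_{0kl} + \beta_{1k} \text{Sequence}_{ij} + \beta_{2k} \text{Age}_{ij} + \beta_{3k} \text{Female}_{ij} + \delta_j". Each probability is that theta divided by the sum of the thetas. The `mu_0kl` "are the intercepts with μ_{0k4} set to 0". On priors: "We will use independent vague $N(0, 1000)$ priors for the regression coefficients"; the list that follows again shows `mu_0kl` with the category index `l`, and `beta_1k`, `beta_2k`, `beta_3k` without it.

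Superiority on item k is declared if Pr(OR_k > 1 | y) is at least 0.975, with OR_k = p1(1 − p2) / [p2(1 − p1)], where p1 is Test and p2 is Control. SAP 5.3 hypothesises superiority on all nine items. Protocol 14.7 plans only descriptive summaries with optional exploratory analysis, but SAP section 1 gives the SAP precedence.

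**The concern.** There are two separate faults.

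First, a covariate affects a multinomial probability only if its coefficient differs between categories. Here the coefficients and the site effect are common to all four, so the promised adjustment for sequence, age, sex and site is not made. Sequence is the term that matters most: answers are recorded as first versus second lens, and protocol 4.2 reports significant carryover in earlier 2×2 studies of this Test lens.

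Second, the modelled categories are not the collected answers. Nothing says how first/second becomes Test/Control, that 'strongly prefer' is merged with 'prefer', or where no preference goes. At stake is a formal superiority rule whose reported odds ratio depends on a coding decision that the SAP does not state.

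**Working it through.** The documents give no power or sample size for the preference items, so there is no plan figure to reproduce. All counts and percentages below are assumptions for illustration.

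**1. Cancellation.** Write eta for the sum of the sequence, age, sex and site terms for one subject. As written, p_l = exp(mu_l + eta) / Σ_m exp(mu_m + eta). The factor exp(eta) appears in the numerator and in every term of the sum, so p_l = exp(mu_l) / Σ_m exp(mu_m).

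Numerically, take intercepts 0.3, 0, −3 and 0 for Test, Control, both and neither. At eta = −2, 0 and 2 the probabilities are the same each time: 0.3971, 0.2941, 0.0146, 0.2941.

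**2. The charitable reading.** Suppose the author meant log(theta_4) = 0 in full, not just its intercept.

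| eta | Test | Control | both | neither | p1/p2 |
|---|---|---|---|---|---|
| −2 | 0.1379 | 0.1022 | 0.0051 | 0.7549 | 1.3499 |
| 0 | 0.3971 | 0.2941 | 0.0146 | 0.2941 | 1.3499 |
| 2 | 0.5325 | 0.3945 | 0.0196 | 0.0534 | 1.3499 |

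The covariates now move the reference category, but p1/p2 stays at exp(0.3). OR_k itself changes through the (1 − p) terms: 1.3499 × 0.8978/0.8621 = 1.41 at eta = −2, and 1.3499 × 0.6055/0.4675 = 1.75 at eta = 2. It cannot cross 1, because sequence still cannot tilt the balance between Test and Control.

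**3. The model does run.** The model was fitted as written by Metropolis sampling to assumed counts of 47 Test, 32 Control and 26 no preference (total 105, the target completers). No preference was coded 'neither', and 'both' was 0.
- OR_k was 1.86 (95% credible interval 0.91 to 3.81) and Pr(OR_k > 1) was 0.954.
- A coefficient common to all categories returned its prior: posterior SD 31.7, against a prior SD of √1000 = 31.6.
- The intercept of the empty 'both' category drifted to about −27 (SD 18), held only by its prior.

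**4. Where no preference goes.** OR_k > 1 means p1(1 − p2) > p2(1 − p1), which reduces to p1 > p2. The success probability therefore depends only on the Test-versus-Control balance. Dirichlet posteriors give, as median OR_k and Pr(OR_k > 1):

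| Coding of no preference | Counts 47/32/26 | Counts 50/30/25 |
|---|---|---|
| 'neither' | 1.86; 0.956 | 2.29; 0.988 |
| 'both' | 1.86; 0.956 | 2.29; 0.988 |
| dropped | 2.18; 0.956 | 2.80; 0.988 |
| split evenly | 1.78; 0.930 | 2.17; 0.975 |

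The first three codings give the same success probability. Only the even split, which nothing in the SAP proposes, changes it.

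**5. Size of the odds ratio by hand.** Assume 42% Test, 28% Control and 30% no preference.
- Kept in the denominator: 0.42 × 0.72 / (0.28 × 0.58) = 0.3024 / 0.1624 = 1.86.
- Dropped: 0.42/0.70 = 0.6 and 0.28/0.70 = 0.4, so 0.6 × 0.6 / (0.4 × 0.4) = 2.25.

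**6. Other slips in the same block.** OR_k is defined for k = 1 to 5 although nine items are listed. The site effect is delta in the predictor but gamma in its distribution.

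**The case against.** The strongest reply is that this is notation on a minor endpoint. The subscripts in this block are visibly unreliable, and the prose makes the intention to adjust clear. Sequence is randomised in blocks of 2, so the two orders should be nearly balanced and an order effect should largely average out of the marginal proportions behind OR_k. Lens preference sits under Other Hypotheses (SAP 5.3), outside the primary and secondary success criteria, and the study was not powered for it.

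Much of this stands. It limits the importance of the point, and no bias from the lost adjustment has been estimated. The notation defence is weaker: the category index is missing from the coefficients in both the predictor and the prior list, while the intercept keeps it in both. A programmer following the SAP would code the inert version.

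A reader might also infer more than the documents support:
- *That the model cannot be fitted.* The priors are proper, so the posterior exists, and step 3 obtained one.
- *That no preference has no possible category and the reference is empty.* Such an answer fits the wording of 'neither' reasonably well, and on that reading the reference is populated. What is missing is a stated mapping.
- *That the coding decides superiority.* Under the three codings 'neither', 'both' and dropped, it does not.

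**Conclusion.** The model is wrong as written in one respect and underspecified in another. The sequence, age, sex and site adjustment in SAP 11.3 has no effect on any modelled probability. Under the most generous reading it still cannot shift the Test-to-Control ratio. This is algebra and needs no assumption beyond the formulas as printed.

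The categories do not match the described responses: 'both' is structurally empty and the place of no preference is left open. The response set is taken from the endpoint text, because the questionnaire itself is not available.

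The practical effect is on the size of the reported odds ratio (1.86 against 2.25 under the assumed 42/28/30 split), not on the superiority decision under the three codings above. With blocked randomisation and an 'Other' endpoint the gain from correction is modest. It should still be made, because the SAP attaches a formal decision rule to an adjustment that does not exist.

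**What to change.** Amend the lens-preference part of SAP 11.3:

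1. Convert first/second lens to Test/Control using the assigned sequence, and collapse the five answers to Test, Control and no preference.
2. Make no preference the reference, with its whole predictor set to 0 and not only its intercept.
3. Give each non-reference category its own coefficients (`beta_1kl`, `beta_2kl`, `beta_3kl`) and its own site effect, and use one symbol for that effect.
4. Keep no-preference answers in the denominator of OR_k.
5. Define OR_k for k = 1 to 9.

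A cumulative-logit model on the five-point scale, oriented to Test, would keep the strength of preference, but it is an optional modelling choice and not needed to repair the fault.

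The cost is SAP wording and model code. No new data are required.
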